5.2.2. Day 8 Assessment

The following assessments will be performed on Day 8 of each cycle, unless otherwise specified:

- Concomitant medication and procedures evaluation
- Vital signs
- CBC, differential and platelet count
- Clinical chemistry panel (including but not limited to sodium, potassium, chloride, glucose, alkaline phosphatase (ALP), AST/SGOT, ALT/SGPT, serum albumin)
- Trough levels of rapamycin will be obtained immediately prior to ABI-009 infusion at Day 15 of second and third cycles of ABI-009.
- Adverse Event assessment

5.2.3. Day 15 Assessment

The following assessments will be performed on Day 15 of each cycle, unless otherwise specified:

- Concomitant medication and procedures evaluation
- Vital signs
- CBC, differential and platelet count
- Adverse Event assessment

5.2.4. Response Assessment

Tumor response will be assessed by CT or MRI scan of the chest, abdomen, and pelvis (CAP); image preparation and evaluation will follow the specifications provided in the RECIST version 1.1. Immune RECIST (irRECIST) will also be obtained. The same modality (CT or MRI) must be used at screening and throughout the study.

CT/MRI scans to be performed at the following frequency:

- ≤2 weeks prior to C1D1 (screening)
- followed by every 6 weeks for the first year; then every 12 weeks until disease progression or unacceptable toxicity. End of Treatment Visit CT/MRI should be performed only for those patients that discontinue treatment for a reason other than disease progression.

An unscheduled scan for suspected disease progression may be performed at any time. However, adherence to the planned imaging schedule is critical regardless of dose delays or unscheduled or missed assessments. Determination of disease progression for clinical management of patients on study will be assessed at the local site. If an initial observation

of objective response (CR or PR) is made, a confirmation scan should be done at 6 weeks after initial observation.

Conditions for Continuation of Treatment in the Presence of Increased Tumor Size by CT scan or MRI Indicating Progressive Disease by RECIST v1.1:

Treatment may be continued if:

1. There are no signs or symptoms indicating unequivocal progression.
2. There is no worsening of ECOG score attributable to progressive disease.
3. There is no tumor growth at critical sites that is life-threatening.
4. Patient signs an informed consent that he/she is aware of alternative therapies but wishes to defer these therapies.
5. There is clinical benefit, as determined by investigator

Table 3. Analyte Listing

Chemistry	Hematology	Coagulation	Urinalysis	Other Labs
Sodium	WBC	PT	Specific gravity	Pregnancy test
Potassium	RBC	PTT	pH	
Bicarbonate	Hemoglobin	INR	Blood	TSH, T3, T4
Chloride	Hematocrit		Protein	HIV
Total protein	MCV		Glucose	HBV sAg
Albumin	MCH		Ketones	HBV cAb
Calcium	MCHC		Microscopic	HCV Ab
Magnesium	RDW			Total Cholesterol
Phosphorus	Platelets			HDL
Glucose	Differential:			LDL
BUN	-Neutrophils			Triglyceride
Creatinine	-Lymphocytes			PD-1\PD-L1
Total bilirubin	-Monocytes			
Alkaline phosphatase	-Eosinophils			
AST (SGOT)	-Basophils			
ALT (SGPT)				
Amylase				
Lipase				

5.3. End of Treatment Visit Assessment

Patient participation is complete after the EOT Visit. The EOT Visit is a safety follow-up visit that is to be performed at least 4 weeks (+ 7 days) after the last dose of ABI-009 or

nivolumab. All efforts should be made to conduct this visit. If it is not possible to conduct the EOT Visit, documentation of efforts to complete the visit should be provided.

The following procedures will be completed at the EOT Visit as designated in the Schedule of Assessments ([Table 2](#)):

- Physical examination (including physical exam, ECOG Performance Status assessment, weight)
- Vital signs (eg, blood pressure, pulse, respiration rate, temperature)
- Laboratory assessments: chemistry, CBC, differential, platelet count, pregnancy test (women of child-bearing potential, includes tubal ligations)
- Imaging Assessment: CT/MRI is to be performed at the end of study visit only for those patients that discontinue treatment for a reason other than disease progression per RECIST v1.1

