End of Treatment	The date of the last dose of ABI-009 or nivolumab which ever is later for an individual patient.
End of Treatment Visit	For a patient is when safety assessments and procedures are performed after the last treatment, which must occur at least 4 weeks (\pm 7 days) after the last dose of ABI-009 or nivolumab whichever is later.
Primary Analysis	For this study will occur after all patients have either completed the study or completed 12 months of treatment. Patients who are still active at the time of the primary analysis may continue on study until disease progression or medication intolerance is observed.
Follow-up Period	The on-study time period after the End of Treatment Visit. All patients that discontinue study drug and have not withdrawn full consent to participate in the study will continue in the follow-up phase for survival and anticancer therapy. Follow up will continue approximately every 12 weeks (+/- 3 weeks), or more frequently as needed, until death, withdrawal of consent, or the study closes, whichever is the earliest. This evaluation may be made by record review and/or telephone contact.
Efficacy Analysis Dataset	All enrolled patients with measurable tumor per RECIST v1.1 at baseline who received at least two doses of ABI-009 and had a follow-up CT scan/MRI (modified treated population)
Full Analysis Set	All enrolled patients who receive at least one dose of ABI-009 (treated population).
Per-protocol Analysis Set	All enrolled patients who do not have any prospectively defined protocol violations.

Progression-free survival	The time from the first dose date to the first observation of a disease progression or death due to any cause.
Recurrence-free survival	The time from the first dose date to the first observation of disease progression or recurrence/progression after surgical resection, or death due to any cause.
Overall survival	The time from the first dose date to the date of death due to any cause.
Overall response rate	The proportion of patients who achieve a confirmed partial response or complete response per RECIST 1.1. Response rates based on a local radiologic assessment
Duration of response	The time from when criteria of response are first met until the first observation of disease progression per RECIST v1.1 or death due to any cause, whichever comes first.

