In Trial 1, where patients were evaluated at baseline and during the trial for thyroid function, Grade 1 or 2 hypothyroidism occurred in 8% (21/268) of patients receiving nivolumab and none of the 102 patients receiving chemotherapy. The median time to onset was 2.5 months (range: 24 days-11.7 months). Seventeen of the 21 patients with hypothyroidism received levothyroxine. Fifteen of 17 patients received subsequent nivolumab dosing while continuing to receive levothyroxine.

Grade 1 or 2 hyperthyroidism occurred in 3% (8/268) of patients receiving nivolumab and 1% (1/102) of patients receiving chemotherapy. The median time to onset in nivolumab-treated patients was 1.6 months (range: 0-3.3 months). Four of five patients with Grade 1 hyperthyroidism and two of three patients with Grade 2 hyperthyroidism had documented resolution of hyperthyroidism; all three patients received medical management for Grade 2 hyperthyroidism.

- **Any other severe or Grade 3 treatment-related adverse reactions**

Other clinically significant immune-mediated adverse reactions can occur. Immune-mediated adverse reactions may occur after discontinuation of nivolumab therapy.

The following clinically significant, immune-mediated adverse reactions occurred in less than 1% of nivolumab-treated patients in Trial 1: pancreatitis, uveitis, demyelination, autoimmune neuropathy, adrenal insufficiency, and facial and abducens nerve paresis.

Across clinical trials of nivolumab administered at doses of 3 mg/kg and 10 mg/kg the following additional clinically significant, immune-mediated adverse reactions were identified: hypophysitis, diabetic ketoacidosis, hypopituitarism, Guillain-Barré syndrome, and myasthenic syndrome.

Nivolumab was discontinued for adverse reactions in 9% of patients. Twenty-six percent of patients receiving nivolumab had a drug delay for an adverse reaction. Serious adverse reactions occurred in 41% of patients receiving nivolumab. Grade 3 and 4 adverse reactions occurred in 42% of patients receiving nivolumab. The most frequent Grade 3 and 4 adverse reactions reported in 2% to less than 5% of patients receiving nivolumab were abdominal pain, hyponatremia, increased aspartate aminotransferase, and increased lipase. Other adverse events that occurred in $\geq 10\%$ of patients were rash, pruritus, cough, upper respiratory tract infection, peripheral edema, increased AST, increased alkaline phosphatase, hyponatremia, increased ALT, and hyperkalemia, with

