3.3. Exclusion Criteria

A patient will not be eligible for inclusion in this study if any of the following criteria apply:

- 1. Known active uncontrolled or symptomatic central nervous system (CNS) metastases. A patient with controlled and asymptomatic CNS metastases may participate in this study. As such, the patient must have completed any prior treatment for CNS metastases ≥ 28 days (including radiotherapy and/or surgery) prior to start of treatment in this study and should not be receiving chronic corticosteroid therapy for the CNS metastases.
- 2. Active gastrointestinal bleeding.
- 3. Pre-existing thyroid abnormality is allowed provided thyroid function can be controlled with medication.
- 4. Uncontrolled serious medical or psychiatric illness. Patients with a “currently active” second malignancy other than non-melanoma skin cancers, carcinoma in situ of the cervix, resected incidental prostate cancer (staged pT2 with Gleason

Score ≤ 6 and postoperative PSA <0.5 ng/mL), or other adequately treated carcinoma-in-situ are ineligible. Patients are not considered to have a “currently active” malignancy if they have completed therapy and are free of disease for ≥1 year).

5. Liver-directed therapy within 2 months of enrollment. Prior treatment with radiotherapy (including radio-labeled spheres and/or cyberknife, hepatic arterial embolization (with or without chemotherapy) or cyrotherapy/ablation) is allowed if these therapies did not affect the areas of measurable disease being used for this protocol.
6. Recent infection requiring systemic anti-infective treatment that was completed ≤14 days prior to enrollment (with the exception of uncomplicated urinary tract infection or upper respiratory tract infection).
7. Uncontrolled diabetes mellitus as defined by HbA1c >8% despite adequate therapy.
8. Unstable coronary artery disease or myocardial infarction during preceding 6 months.
9. Receiving any concomitant antitumor therapy.
10. Patients with history of interstitial lung disease and/or pneumonitis, or pulmonary hypertension.
11. Use of strong inhibitors and inducers of CYP3A4 within the 14 days prior to receiving the first dose of ABI-009. Additionally, use of any known CYP3A4 substrates with narrow therapeutic window (such as fentanyl, alfentanil, astemizole, cisapride, dihydroergotamine, pimozide, quinidine, terfanide) within the 14 days prior to receiving the first dose of ABI-009.
12. Known Human Immunodeficiency Virus (HIV).

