4. TABLE OF EVENTS

The schedule of assessments in Table 2 outlines the specific time points for study assessments.

Table 2. Schedule of Assessments

Assessment ^a	Screening ^b (Day -14 to -1)	Cycle 1 through Last Cycle (Treatment Period)			End of Treatment (EOT) Visit ^d	Follow-up Period ^e
		Day 1 ^c	Day 8	Day 15		
General Assessments						
Informed Consent	X					
Demographics	X					
Medical History	X					
Physical Examination	X	X			X	
Vital Signs, Height and Weight	X	X ^f	X ^f	X ^f	X ^f	
BSA Calculation		X ^j				
Prior/Concomitant Medication Evaluation ^g	X	X	X	X	Until 28 days after the last dose of IP	
Prior/Concurrent Procedures Evaluation ^g	X	X	X	X	Until 28 days after the last dose of IP	
ECOG PS	X	X			X	
Pregnancy Test ^h	X				X	
ECG (12 lead) ⁱ	X					
Survival status						X
Adverse Events		Continuous starting from signing of Informed Consent until 28 days after last dose of IP				
Dexamethasone (every cycle)			X			
Nivolumab Dosing		X				
ABI-009 Dosing: To Start after 2nd Nivo dose			X	X		
Local Laboratory Assessments						
Clinical Chemistry Panel	X	X	X	X	X	
CBC, Differential, Platelet Count	X	X	X	X	X	

Assessment ^a	Screening ^b (Day -14 to -1)	Cycle 1 through Last Cycle (Treatment Period)			End of Treatment (EOT) Visit ^d	Follow-up Period ^e
		Day 1 ^c	Day 8	Day 15		
PT, PTT, INR	X					
Urinalysis	X					
Thyroid function	X	X				
HIV, HBV sAg, HBV cAb, HCV Ab	X					
Fasting Lipids	X	X				
Trough rapamycin level ^k						
Immunohistochemistry for PTEN mutation in archived tumor	X					
Imaging and Efficacy Assessments						
CT/MR ^l	X	Every 6 weeks after C1 D1 for the first year, then every 12 weeks thereafter			X	

- a. Unless otherwise specified, visits must occur within \pm 2 days of the planned visit date.
- b. Screening evaluations to be obtained \leq 14 days prior to enrollment unless specified otherwise.
- c. Day 1 evaluations can be omitted if screening evaluations are performed within 72 hours of Cycle 1 Day 1 except for thyroid and fasting lipids every 12 weeks.
- d. End of Treatment Visit must occur at least 4 weeks (\pm 7 days) after the last dose of ABI-009.

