5.2.1. Day 1 Assessment

The following assessments will be performed on Day 1 of each cycle, unless otherwise specified:

- Physical examination
- Weight assessment
- BSA calculation (Calculated ONLY on C1/D1; to be recalculated only if the weight changes by > 10% in subsequent cycles)
- Concomitant medication and procedures evaluation
- Vital signs (temperature, systolic and diastolic blood pressure, and pulse)
- ECOG performance status
- Clinical chemistry panel (including but not limited to sodium, potassium, chloride, glucose, alkaline phosphatase (ALP), AST/SGOT, ALT/SGPT, serum albumin)
- CBC, differential and platelet count
- Thyroid function (every 12 weeks)
- Fasting lipids (every 12 weeks)
- Adverse Event assessment

Day 1 evaluations for Cycle 1 may be omitted if screening evaluations are performed within 72 hours of Cycle 1 Day 1. Laboratory assessments: chemistry, hematology,

coagulation, urinalysis, pregnancy test (women of child-bearing potential, includes tubal ligation)

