8. STATISTICAL CONSIDERATIONS

8.1. Study Endpoints

Primary Endpoint:

- MTD

Secondary Endpoint(s):

- Disease control rate (DCR), ORR (CR+ PR)
- Progression-free survival
- Progression-free survival rate at 3,6,9,12 months
- Overall survival
- Incidence and grade of treatment-emergent AEs

Exploratory Endpoint(s):

- Correlation of response based on RECIST v1.1 and irRECIST
- Correlation between response and PD-L1 expression in patients' tumors
- Correlation between DCR and PTEN mutation in patient's archived tumor

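### With no thyroid test at the end-of-treatment visit, treated patients who stop before day 85 have no scheduled post-baseline thyroid value

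*Combined protocol and SAP*

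**What the plan says.** Table 2 marks thyroid function at screening and Day 1 only; the Day 8, Day 15, EOT and follow-up cells are blank. The Day 1 mark does not mean every cycle. Section 5.2.1 lists "Thyroid function (every 12 weeks", and footnote c of Table 2 lets Cycle 1 Day 1 evaluations be skipped after recent screening "except for thyroid and fasting lipids every 12 weeks".

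The EOT laboratory list in Section 5.3 reads "Laboratory assessments: chemistry, CBC, differential, platelet count, pregnancy test (women of child-bearing potential, includes tubal ligations". Table 3 places TSH, T3 and T4 under other laboratory tests, so the word chemistry in that list does not bring them in. After the EOT visit, follow-up covers survival and subsequent anticancer therapy only and may be done by telephone or record review (Section 5.4).

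The safety population is the Full Analysis Set, defined in the list of terms as "All enrolled patients who receive at least one dose of ABI-009 (treated population". ABI-009 starts on Day 8 of Cycle 2 (Section 6.1). Section 8.1 lists "Incidence and grade of treatment-emergent AEs" as a secondary endpoint.

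**The concern.** Section 1.3.3 gives reason to look for thyroid events before the first scheduled test. For hyperthyroidism, "The median time to onset in nivolumab-treated patients was 1.6 months (range: 0-3.3 months"; for hypothyroidism the median is 2.5 months. The same section warns: "Immune-mediated adverse reactions may occur after discontinuation of nivolumab therapy". The EOT visit, which Section 5.3 describes as a safety follow-up, is the last visit with blood sampling and so the last scheduled opportunity to test.

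Two things are at stake. The first is ascertainment. The thyroid rates quoted from the nivolumab melanoma study (Trial 1) came from patients tested at baseline and during that study. A lower rate here could reflect less testing rather than less toxicity. Section 8.2 also plans baseline-to-worst grade shifts for a selection of laboratory parameters. If thyroid is among them, early stoppers would have no scheduled value to enter.

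The second is patient care. Hypothyroidism is treatable, and without a scheduled test it may be found late. This applies also to patients admitted with controlled thyroid disease ("Pre-existing thyroid abnormality is allowed provided thyroid function can be controlled with medication"), in whom worsening would be picked up only if symptoms prompted a test.

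**Working it through.** The plan gives no figure of its own on this point. The check is calendar arithmetic plus the event rates quoted in Section 1.3.3.

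**Inputs**

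- Cycle length 21 days; first ABI-009 dose at Cycle 2 Day 8 (Section 6.1; synopsis, Study Treatment).
- Thyroid testing every 12 weeks, which is 84 days or four cycles (Section 5.2.1; Table 2).
- EOT visit 4 weeks ± 7 days after the last dose (Sections 2.4 and 2.5; Section 5.3 prints + 7 days).
- Trial 1: hypothyroidism 21/268, median onset 2.5 months; hyperthyroidism 8/268, median onset 1.6 months; median exposure 5.3 months (Section 1.3.3).
- Evaluable patients: 12–18 in Phase 1 and 22–28 in Phase 2 (Section 8.2).

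**Calendar, with no dosing delays:** study day = 21 × (cycle − 1) + day

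| Visit | Study day |
|---|---|
| C2D8, first ABI-009 dose | 29 |
| C3D8 | 50 |
| C4D15 | 78 |
| C5D1 | 85 |

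Scheduled thyroid tests fall on days 1, 85, 169 and 253. Day 1 is the pre-dose baseline, so day 85 is the first post-baseline value. The gap runs from day 29 to day 84.

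**Onset, at 30.44 days per month**

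- Hyperthyroidism: 1.6 × 30.44 = day 49.
- Hypothyroidism: 2.5 × 30.44 = day 76.
- With 30 to 31 days per month the ranges are 48.0–49.6 and 75.0–77.5. Both medians precede day 85.

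**When an EOT test would fall**

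| Last dose | EOT at 28 days | Range at ± 7 days |
|---|---|---|
| Day 29 | 57 | 50–64 |
| Day 50 | 78 | 71–85 |
| Day 78 | 106 | 99–113 |

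An EOT test would follow the median hyperthyroidism onset for every last dose in the gap. At the nominal 28 days it would also follow the median hypothyroidism onset for last doses from C3D8 (day 50) onward.

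**Expected events**

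- Patients: 12 + 22 = 34 to 18 + 28 = 46.
- Hypothyroidism in all patients: 21/268 = 7.8%, giving 2.7 to 3.6 events.
- Hyperthyroidism in all patients: 8/268 = 3.0%, giving 1.0 to 1.4 events.
- Either type: 29/268 = 10.8%.
- For each 10% of patients stopping in the gap (an assumed unit): 3.4 to 4.6 patients, and 0.108 × 3.4 to 0.108 × 4.6 = 0.37 to 0.50 events.

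**How many might stop early.** The documents do not say. In Trial 1 the median exposure of 5.3 × 30.44 = 161 days means fewer than half had stopped by week 12, but those were melanoma patients dosed every 2 weeks. The pembrolizumab sarcoma study in Section 1.1.2 had 12-week PFS of 55% in soft tissue sarcoma and 28% in bone sarcoma, so about 45% and 72% had progressed or died by then. Neither transfers directly. The drug or schedule differs, this trial admits many tumor types, treatment beyond progression is allowed, and patients who progress before ABI-009 are replaced.

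**Later stoppers.** A patient whose last dose is C8D15 (day 162) was last tested on day 85. By a day-190 EOT visit, 190 − 85 = 105 days have passed without a scheduled test.

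**The case against.** The schedule reading is not in dispute; the case against concerns consequence.

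- **Few events.** The 0.37 to 0.50 per 10% stopping early is probably too high as a count of losses. Trial 1 rates accrued over a median of 5.3 months with hypothyroidism onsets up to 11.7 months, and symptomatic cases would still be found. This stands and keeps the point minor.
- **The affected group is somewhat smaller than the last-dose window suggests.** Assessments precede dosing, so a patient whose last dose is C4D15 but who attends C5D1 has the day-85 test. The second scheduled scan falls at about day 85, so some who stop for progression then are covered. This stands; the gap applies to those who stop before attending C5D1.
- **An EOT test helps least for the earliest stoppers.** A patient stopped at the first scan (about day 43), with a last dose on day 36 or 43, has a nominal EOT visit on day 64 or 71, before the hypothyroidism median. At the extreme, day 50 against day 49 leaves a one-day margin for hyperthyroidism; with the + 7 days printed in Section 5.3 the earliest visit is day 57. Six of eight Trial 1 hyperthyroidism cases had documented resolution, so a single late test may miss some. This stands, but the present schedule gives these patients no test at all.
- **Other cover exists.** Twelve-weekly testing meets the general instruction in Section 6.3.1 to monitor periodically. EOT includes examination, vital signs and chemistry, and adverse events are collected for 28 days after the last dose. The endocrinopathy algorithm is a figure not shown, so any testing it requires cannot be seen. None of the visible text schedules a thyroid test at EOT.
- **Conditional harm.** The shift-table argument holds only if thyroid is a selected parameter, which the documents do not state. The onset data come from 2-weekly monotherapy in melanoma.

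**Conclusion.** The concern holds as a low-cost improvement, not a threat to the trial's conclusions. A treated patient who stops from day 29 and before the day-85 visit has no scheduled post-baseline thyroid value, although the protocol's own onset medians fall earlier than that visit. The expected number of thyroid events in this group is below one for each 10% of patients who stop there. The number actually missed cannot be estimated from the documents. The primary endpoint is essentially untouched, because all Trial 1 thyroid events were Grade 1 or 2 and call for no nivolumab dose change. Under-counting of low-grade events and late detection of treatable hypothyroidism are the realistic consequences.

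The day counts assume undelayed dosing and a 12-week clock starting at Cycle 1 Day 1. The event counts assume Trial 1 rates apply to this combination.

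**What to change.** Add TSH, T3 and T4, already listed in Table 3, to the EOT column of Table 2 and to the laboratory list in Section 5.3. In the safety report, give the number of patients with any post-baseline thyroid test next to the thyroid adverse event counts.

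The cost is a one-line change in each place and one extra assay per patient on blood already drawn. Every treated patient who attends the EOT visit would then have at least one scheduled post-baseline value. Testing every 6 weeks for the first 12 weeks, which would add Cycle 3 Day 1 (day 43), is optional and not needed to close the gap.
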